3 OBJECTIVES AND ENDPOINTS

OBJECTIVES	ENDPOINTS	JUSTIFICATION FOR ENDPOINTS
Primary		
Examine the efficacy of low-frequency rTMS for the treatment of AVH in patients with a schizophrenia spectrum disorder.	Our primary outcome will be the score of the Hallucination Change Scale (HCS) (Hoffman et al., 2003). Response criteria: a) Clinically significant improvement in AVH is	The HCS is used as our primary outcome measure. The scale will be anchored at baseline using the narrative description of AVHs provided by the patient for the prior 24 hours, which will be assigned a score of 10. For subsequent assessments, the HCS ranges from 0-20 (with a score of 20

OBJECTIVES	ENDPOINTS	JUSTIFICATION FOR ENDPOINTS
	defined as a score of <8 on the HCS (Hoffman et al., 2013) b) Drop-outs: defined as patients who discontinue treatment before completing the 4 rTMS sessions.	corresponding to hallucinations twice as severe as baseline) (Hoffman et al., 2003; Hoffman et al., 2013). The HCS is a frequently used assessment for AVH in schizophrenia (Hoffman et al., 2003; Hoffman et al., 2013; Philipp Homan et al., 2011; P Homan et al., 2012). It is a feasible and time-efficient measure to assess severity of AVH on a daily basis and to evaluate improvement of AVH severity.
Secondary		
Monitor qualitative changes in AVH during the course of the rTMS treatment.	a) the qualitative content of AVH are assessed using the BAVQ-R to monitor changes in the content of AVH.	The BAVQ-R (CHADWICK, LEES, & BIRCHWOOD, 2000) is a self-report measure of patient's beliefs, emotions and behavior about AVH. This allows to assess changes in the quality of AVH over time and monitor if severity increases to the point of being dangerous for the patient or others (suicidal or homicidal tendencies).
Assessment of AVH as part of positive symptoms.	b) positive symptoms BPRS-subscale including "Hallucinatory Behavior", "Conceptual Disorganization", "Suspiciousness", and "Unusual Thought Content".	The positive symptoms BPRS-subscale is a well validated, often in studies used measure to assess positive symptoms including AVH (Robinson et al., 2015; Shafer, 2005).

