6.4 STUDY INTERVENTION COMPLIANCE

Compliance to study intervention is firstly confirmed by the patient signing the informed consent form. If patients do not want to continue treatment and finish all 4 rTMS sessions together with pre- and post-imaging and interviews, they will be excluded from the study which will be mentioned in the case report form. The data collected up to this point will not be included in the analysis because the primary outcome is the outcome measure of the HCS for which all three measures (baseline, after the last rTMS session, post-MRI) are necessary to reasonably estimate the symptom trajectory.

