9.4 STATISTICAL ANALYSES

9.4.1 GENERAL APPROACH

Descriptive statistics will include all patients who completed the study. Patient groups (stratified according to either their sham or real rTMS treatment) will be compared concerning age, sex, socio economic status, general psychopathology (CGI, GAF), severity of AVH (BPRS-subscale, BAVQ-R), and cognitive outcome (rBANS). In particular, mean (standard deviation) together with the range (min, max) will be assessed for the two groups.

Inferential statistics: the p-value will be set to 5% and therefore every value below this threshold is considered significant. Effect sizes will be calculated as well to evaluate if we are dealing with a clinically important effect. Covariates will be included in the analyses such as age and sex.

General assumptions of heterogeneity and normality will be assessed before any subsequent analysis. Based on this either parametric or non-parametric tests will be chosen.

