9.4.2 ANALYSIS OF THE PRIMARY EFFICACY ENDPOINT(S)

Our primary goal is to examine if real rTMS for the treatment of AVH is superior to sham rTMS. Therefore, we test if symptoms decreased in patients who received 4 sessions of low-frequency rTMS for one day.

For this purpose, repeated measures ANCOVAs will be implemented with time of measurements as the within-subject factor, group (treatment vs. placebo) as between subject's factor, and baseline HCS scores as covariate.

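### The primary test is not fixed in advance: checks of the collected data decide between parametric and non-parametric methods, and no check, cut-off or fallback is named

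*Combined protocol and SAP*

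**What the plan says.** Section 9.4.1 (General Approach) sets a rule for all inferential analyses: "General assumptions of heterogeneity and normality will be assessed before any subsequent analysis", followed by "Based on this either parametric or non-parametric tests will be chosen". (Heterogeneity presumably means homogeneity of variance.) The same section leaves the covariate list open, "Covariates will be included in the analyses such as age and sex", and sets the significance level: "the p-value will be set to 5% and therefore every value below this threshold is considered significant".

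Section 9.4.2 then gives the primary analysis: "repeated measures ANCOVAs will be implemented with time of measurements as the within-subject factor", with group as the between-subject factor and "baseline HCS scores as covariate". It does not say whether the group effect or the group-by-time interaction is the primary contrast.

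Section 6.4 fixes the rating times: "all three measures (baseline, after the last rTMS session, post-MRI) are necessary to reasonably estimate the symptom trajectory". So there are two post-baseline ratings. Section 3 anchors the baseline description, "which will be assigned a score of 10", and later ratings run from 0 to 20.

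For the clinical endpoints, no section names a normality or variance check, a cut-off, the variable to be checked, whether the choice is made blind to arm, or a non-parametric test. The only non-parametric method described is the permutation tool for the diffusion images in section 9.4.3.

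**The concern.** A confirmatory p-value has its nominal meaning only if the test was fixed before the data were seen. Here the branch depends on the data, and the second branch is blank. Mann-Whitney, Wilcoxon and Friedman tests cannot handle a between-group factor, a repeated factor and covariates at once. An analyst who moves to one of them must therefore also decide whether to use the first post-treatment rating, the last, or their mean, and must drop the covariates.

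The branch could well be used. Every patient starts at exactly 10, so unchanged patients share one value, and the scale is bounded.

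The choice can also decide the verdict. With simulated data at 20 per arm, a t-test and a Mann-Whitney test on the same score disagreed about significance in 2.0-3.4% of trials under the null and in 4.9-14.3% at d = 0.9, depending on the distribution. Section 9.2 says that a detected effect may be the basis for a larger study, so that verdict will be acted on.

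**Working it through.** **The plan's own figure.** Section 9.2 gives d = 0.9, 80% power, alpha 5% and 20 per arm, from a two-sample t-test. Normal approximation, two-sided: n = 2 × (1.960 + 0.842)² / 0.9² = 2 × 7.85 / 0.81 = 19.4, rounded up to 20 per arm. The noncentral t gives 20.39 per arm, and power at 20 per arm is 79.2%. The stated 40 is reproduced within rounding. One-sided testing would need only 16 per arm, so a two-sided test is assumed below. The power basis is neither the repeated-measures model nor any rank test.

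**Baseline covariate.** With baseline HCS equal to 10 for everyone, the design matrix [1, group, baseline] has rank 2 of 3. The covariate adjusts for nothing.

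**How often the switch would occur.** This depends on the check and the distribution, and the documents give neither. One Shapiro-Wilk test on residuals at 5%, in 20,000 simulated trials per setting:

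| Assumed distribution | Sent to rank test |
|---|---|
| Normal | 5% |
| t with 3 df | 54% |
| Exponential-type skew | 98% |
| Bounded 0-20, 30% set to exactly 10 | 59% |

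A stricter set of six checks (Shapiro-Wilk per arm and rating, Levene per rating), with any failure triggering a switch, sends about 25% of normal data sets to the rank branch. With independent checks it would be 1 − 0.95⁶ = 26.5%. If about half of patients stay at exactly 10, nearly all data sets switch.

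**Type I error, 20 per arm.** The two-rating runs assume a correlation of 0.7.

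| How the rule is used | Type I error |
|---|---|
| One test fixed in advance (t or Mann-Whitney) | 4.4-5.2% |
| One residual check, one fixed fallback, strictly applied | 5.0-5.7% |
| Same two tests, smaller p-value taken | 6.0-6.6% |
| Failed check (six-check set), smallest of three rank p-values taken | about 6-8% |
| Best of four p-values, whatever the checks show | about 9% |

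The three rank tests are on the first post-treatment rating, the last rating and their mean. The fourth p-value is the t-test on the mean. The last two rows rise with the share of unchanged patients, because nearly every trial then fails a check; individual runs of the last row gave 8.9-10.1%.

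**Power at d = 0.9, normal data, correlation 0.7.** The mean of two ratings has variance (1 + 0.7)/2 = 0.85 of a single rating. The effect size on the mean is therefore 0.9/√0.85 = 0.976, and the noncentral t gives about 85% power at 20 per arm. By simulation:

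| Test | Power |
|---|---|
| t-test, mean of both ratings | about 85% |
| Mann-Whitney, mean of both ratings | about 83% |
| Mann-Whitney, last rating only | about 77% |

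With correlation 0.5-0.7 and age and sex explaining 0-30% of the variance, the adjusted linear model has 84-98% power and Quade's rank ANCOVA on the mean 82-97%.

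**The case against.** The strongest reply is that section 9.4.1 ties the choice to the assumption check, not to the p-values. Followed literally with a single fallback, it costs at most about 0.7 points of type I error (5.7% against 5%). The trial also calls itself an exploratory pilot (sections 5.5 and 9.2). Both points stand, and they limit the weight of the issue.

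Four stronger readings are tempting, and the documents do not support them.

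- A reader might infer that the false-positive rate nearly doubles. That needs an analyst who runs four tests and keeps the best, and the plan does not say this.
- A reader might infer that a switch is almost certain. Rates near 100% rest on an assumed share of unchanged patients or an assumed skewed distribution, and the 25% for normal data rests on an assumed set of six checks. The plan names no check and gives no HCS distribution.
- A reader might infer that a rank fallback throws away half of the primary data. The plan never says that its fallback would use one rating. Even if it did, at correlation 0.7 the information lost is 1 − 0.85 = 15%.
- A reader might infer that the planned model has no rank counterpart, so that the hypothesis itself changes. Rank ANCOVA and rank-based longitudinal methods come close, and section 9.1 words the null as lack of superiority on HCS, not as a difference in means.

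The reply does not supply the missing fallback. Strict application cannot be verified when the check, the cut-off and the alternative test are all unwritten.

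**Conclusion.** The point holds as a gap in pre-specification. The primary test, the rating or ratings it uses and the covariates can all change after the data are examined. The likely inflation is small: about 5.0-5.7% under strict use with one fallback, and about 6-8% when the rank test and rating are left open and the smallest is taken. Power differs by about 2 points between the t-test and the rank test on the same mean, and by about 8 points if the fallback also drops a rating (85% against 77%). A fixed t-test keeps its level in every distribution tried, so the switch protects little.

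These sizes rest on assumed distributions, an assumed correlation and an assumed two-sided test; the documents give no SD or distribution for HCS. The conclusion that the test is not fixed rests only on the text of sections 9.4.1 and 9.4.2.

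**What to change.** For the primary endpoint, delete the sentence that lets the checks choose the test. State instead that, whatever the checks show:

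- the primary analysis is the linear model on the two post-baseline HCS ratings;
- the single primary contrast is the group effect averaged over both ratings;
- age and sex are the only covariates, and baseline HCS is removed because it is constant.

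In patients with both ratings, this is the regression of each patient's mean rating on group, age and sex, with 40 − 4 = 36 residual degrees of freedom. Report one named rank-based analysis, such as Quade's rank ANCOVA on that mean, as a sensitivity analysis only.

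A re-randomisation p-value is optional. If it is used, the SAP should say how replaced patients enter the blocks, because section 7.2 allows replacement and section 9.3 analyses completers only.

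The cost is a few sentences of SAP wording and a little code. N stays 40 and alpha stays 5%.

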9.4.2 ANALYSIS OF THE PRIMARY EFFICACY ENDPOINT(S)

Our primary goal is to examine if real rTMS for the treatment of AVH is superior to sham rTMS. Therefore, we test if symptoms decreased in patients who received 4 sessions of low-frequency rTMS for one day.

For this purpose, repeated measures ANCOVAs will be implemented with time of measurements as the within-subject factor, group (treatment vs. placebo) as between subject's factor, and baseline HCS scores as covariate.

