1 PROTOCOL SUMMARY

1.1 SYNOPSIS

Title: Boost rTMS for AVH – Therapeutic Response and Neurobiological Prediction Markers in Auditory Verbal Hallucinations

Study Description: This is a randomized, placebo controlled, double-blind clinical trial. We aim to examine the efficacy of repeated transcranial magnetic stimulation (rTMS) for the treatment of auditory verbal hallucinations (AVH) in patients with schizophrenia who are not taking antipsychotic medication. We employ a novel, accelerated protocol with only 4 sessions of low-frequency rTMS in one day. The effects of this accelerated protocol will be compared to the sham stimulation. Additionally, we will examine the effects of rTMS on a neurophysiological level by evaluation mechanism of action in the temporo-parietal lobe.

Objectives: Primary Objective:
Examine the efficacy of low-frequency rTMS for AVH in patients with a schizophrenia spectrum disorder.

Secondary Objectives:
Examine the effects of rTMS on the quality of AVH, positive symptoms, general psychopathology, and the global level of functioning of these patients. Last, confirm that rTMS has no side effects on cognitive functioning.

Determine the neuroimaging-related biomarkers associated with response to rTMS using the baseline imaging parameters (rCBF, resting fMRI, T1, and DTI) to predict response to rTMS treatment. Further,

compare pre- and post-treatment imaging parameters (rCBF, resting fMRI, T1, and DTI) to characterize rTMS effects on AVH.

Endpoints:

Primary Endpoint:

- AVH assessed using the Hallucination Change Scale (HCS) at baseline (first visit), after the last TMS session, after the post-MRI.

Secondary Endpoints:

- a) Assessment of the qualitative content of hallucinations will be assessed using the revised Beliefs About Voices Questionnaire (BAVQ-R)
- b) Assessment of AVH as part of positive symptoms will be assessed with the Brief Psychiatric Rating Scale (BPRS)-subscale that includes "Hallucinatory Behavior", "Conceptual Disorganization", "Suspiciousness", and "Unusual Thought Content".
- c) Global functioning will be assessed using the Clinical Global Impression (CGI) and General Assessment of Functioning (GAF) questionnaires.
- d) Cognitive functioning will be assessed using the Repeatable Battery for the Assessment of Neuropsychological Status (rBANS).

Neurophysiological changes using magnetic resonance imaging (MRI) are investigated as predictors for rTMS treatment response.

Study Population:

N = 40

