8 STUDY ASSESSMENTS AND PROCEDURES

8.1 EFFICACY ASSESSMENTS

Rating

All assessments will be performed by trained raters.

Time frame

Screening procedures / evaluation must be done on the same day or the day before inclusion of the patient into the study. The reason for this is that we assess rTMS effect independently of potentially influencing antipsychotic medication effects. Therefore, patients cannot start with antipsychotic medication treatment parallel to the rTMS treatment. Clinical interviews will be conducted by trained staff.

Imaging

MRI acquisition will consist of the following: On the day of imaging, the patient will be transported to the North Shore University Hospital 3T Siemens Prisma MRI suite. The patient will undergo an approximately 55 minutes long acquisition session. All subjects will receive structural (e.g., T1) and functional (e.g. resting BOLD fMRI, DTI, and ASL) MRI exams. During the anatomical images, the participating subject will be asked not to move, during resting state fMRI, the subject will be asked to open their eyes and to think of nothing in particular, but to stay awake. The total scanning time will be approximately 55 minutes.

Assessment of instruments

The primary outcome measure is the improvement of AVH measured with the HCS.

The secondary outcome measures are:

- Qualitative outcome of the BAVQ-R
- AVH as part of positive symptoms measured with the respective BPRS-subscale
- Global functioning assessed using the CGI and GAF
- Cognitive functioning assessed using the rBANS

Structural and functional neurophysiological characteristics are investigated as predictors for rTMS treatment response.

Outcome criteria

Responder criteria:

- a. Clinically significant improvement is defined as a score of <8 on the HCS (Hoffman et al., 2013)
- b. Drop-outs: defined as patients who discontinue treatment before completing the 4 rTMS sessions.

Premature exits:

- a. Consent for study participation is withdrawn before 4 rTMS treatments have been administered, or
- b. rTMS is discontinued for clinical or other reasons before 4 rTMS have been administered, or
- c. Patient misses more than two treatments in total.

Both drop-outs and premature exits in this study will be analyzed as last observation carried forward.

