9 STATISTICAL CONSIDERATIONS

9.1 STATISTICAL HYPOTHESES

Primary Efficacy Endpoint(s):

H0: Real rTMS has no superior effect over sham rTMS in reducing severity of AVH in schizophrenia (HCS score).
H1: Real rTMS has a superior effect over sham rTMS in reducing severity of AVH in schizophrenia (HCS score).

Secondary Efficacy Endpoint(s):

1. H0: Real rTMS has no superior effect over sham rTMS in reducing quality of AVH in schizophrenia (BAVQ-R score).
H1: Real rTMS has a superior effect over sham rTMS in reducing quality of AVH in schizophrenia (BAVQ-R score).
2. H0: Real rTMS has no superior effect over sham rTMS in reducing positive symptoms including AVH in schizophrenia (BPRS-subscale).
H1: Real rTMS has a superior effect over sham rTMS in reducing positive symptoms including AVH in schizophrenia (BPRS subscale).
3. H0: Real rTMS has no superior effect over sham rTMS in reducing severity of general psychopathology in schizophrenia (CGI score).
H1: Real rTMS has a superior effect over sham rTMS in reducing severity of general psychopathology in schizophrenia (CGI score).
4. H0: Real rTMS has no superior effect over sham rTMS in reducing global functioning in schizophrenia (GAF score).
H1: Real rTMS has a superior effect over sham rTMS in reducing global functioning in schizophrenia (GAF score).
5. H0: Real rTMS compared to sham rTMS does not impact cognitive functioning (RBANS).

H1: Real rTMS compared to sham rTMS does not impact cognitive functioning (RBANS).

6. H0: Response to rTMS is not predicted by neurophysiological characteristics.

H1: There are specific neurophysiological markers that predict response to rTMS.

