9.4.3 ANALYSIS OF THE SECONDARY ENDPOINT(S)

Our secondary goal is to test if rTMS improves also the quality of AVH (BAVQ-R), positive symptoms (BPRS-subscale), general psychopathology (CGI), and global functioning (GAF). Further, we want to confirm that rTMS has no impact on cognitive functions (rBANS).

Therefore, we will compute a number of repeated ANCOVAs with time of measurements as the within-subject factor, group (treatment vs. placebo) as between subject's factor, and baseline BAVQ-R scores, the positive symptom BPRS-scale, the CGI, and GAF scores as covariates, respectively. Patients who drop out of the study will not be included in the analyses. Further, we will compare the rBANS scores of baseline with the outcome scores within patients.

Additionally, we want to test if baseline neuroimaging biomarkers can predict response to rTMS. Therefore, voxel-wise multiple regression analyses in our neuroimaging measures will be performed to reveal areas and networks which correlate with the baseline scores of the HCS. We will calculate structural and functional connectivity analyses.

Preprocessing, and overview of the neuroimaging measures:

Baseline metabolic neuronal activity

The treatment effect will be monitored by assessing the baseline resting metabolic neuronal activity measured by ASL (Philipp Homan et al., 2011; Kindler et al., 2012; Orosz et al., 2012). Additionally, variations in resting CBF may be used as covariates of nuisance in all the analysis steps described so far.

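### Baseline HCS is 10 for every patient, so it cannot serve as the covariate in 9.4.2 or the imaging target in 9.4.3; and 9.4.2 does not name the term that tests H1

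*Combined protocol and SAP*

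**What the plan says.** - **The scale (section 3).** The HCS is anchored at baseline on the "narrative description of AVHs provided by the patient for the prior 24 hours, which will be assigned a score of 10". Only later ratings range from 0 to 20. No other section gives a different baseline value.
- **Primary model (9.4.2).** A repeated-measures ANCOVA with time as the within-patient factor, real versus sham as the between-patient factor, "and baseline HCS scores as covariate". No group effect, interaction, contrast or time point is named as the test of H1.
- **Time points.** The synopsis gives the primary endpoint as "AVH assessed using the Hallucination Change Scale (HCS) at baseline (first visit), after the last TMS session, after the post-MRI". Section 6.4 adds that "all three measures (baseline, after the last rTMS session, post-MRI) are necessary to reasonably estimate the symptom trajectory".
- **Imaging (9.4.3).** The stated purpose is to find out whether baseline imaging predicts response, but the voxel-wise regression looks for "areas and networks which correlate with the baseline scores of the HCS". The synopsis describes the aim as using baseline imaging "to predict response to rTMS treatment", and hypothesis 6 in 9.1 also concerns response.
- **Response (8.1).** "Clinically significant improvement is defined as a score of <8 on the HCS".

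**The concern.** A covariate that takes one value for everyone carries no information. The severity adjustment that 9.4.2 appears to promise is therefore not delivered, and the imaging regression has nothing to correlate with.

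The larger matter is that the primary test is not fixed. Section 9.1 states H1 as real against sham, and 9.4.2 opens with that aim. It then describes the test as whether symptoms fell in those given rTMS, which is a within-group question. Using baseline as a covariate implies that time has two levels, both after treatment. The synopsis and 6.4 list three HCS measures, which suggests that baseline is a time level. These readings lead to different tests with very different power. If the choice is made after the data are seen, the 5% threshold in 9.4.1 no longer holds.

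**Working it through.** **The plan's own figure (9.2).** A two-sided two-sample t-test with d = 0.9, 80% power and α = 5% needs n = 20.39 per arm. At 20 per arm the power is 79.2%. The normal approximation gives 20 per arm. The planned 40 is reproduced to within rounding. That calculation is for a t-test, so it does not show which ANCOVA term is primary.

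**Rank of the model.** Baseline HCS = 10 × intercept.
- Intercept, group, baseline HCS: rank 2 with 3 columns.
- With age and sex added (9.4.1): rank 4 with 5 columns. Without baseline HCS: rank 4 with 4 columns.
- Imaging regression (intercept, baseline HCS): rank 1 with 2 columns. The correlation of any imaging measure with a constant is 0/0.

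**Power by candidate term.** Inputs: 20 per arm and d = 0.9 from 9.2. Assumed, because the documents do not give them: equal variance at the two post-treatment ratings, and a correlation ρ between them of 0.5, 0.7 or 0.9. No covariates are included.

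*Group effect.* The mean of two ratings has variance (1 + ρ)/2 in SD² units, so the effective size is d/√((1 + ρ)/2):
- ρ = 0.5: 0.9/√0.75 = 1.04, power 89.3%
- ρ = 0.7: 0.9/√0.85 = 0.98, power 85.3%
- ρ = 0.9: 0.9/√0.95 = 0.92, power 81.2%

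Adding the constant baseline as a time level changes each patient's mean only to (10 + y₁ + y₂)/3. The test of the group effect is therefore identical either way.

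*Group-by-time, two levels.* This tests the difference between the effects at the two ratings, 0.9 − 0.9 = 0. Its power is the significance level, 5%.

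*Group-by-time, three levels.* Simulated with the Greenhouse-Geisser correction.

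| Term | ρ = 0.5 | ρ = 0.7 | ρ = 0.9 |
|---|---|---|---|
| Group effect, d = 0.9 at both | 89% | 85% | 81% |
| Three-level group-by-time, d = 0.9 at both | 82% | 83% | 81% |
| Two-level group-by-time, d = 0.9 at both | 5% | 5% | 5% |
| Group effect, d falling from 0.9 to 0.45 | 67% | 62% | 57% |
| Three-level group-by-time, d falling from 0.9 to 0.45 | 70% | 73% | 73% |
| Two-level group-by-time, d falling from 0.9 to 0.45 | 28% | 43% | 87% |

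**Type I error of choosing afterwards.** The share of null trials in which at least one of the three terms has p < 0.05 is 10.2/9.8/9.7% (60,000 simulated trials per value of ρ). As a check, the sum and the difference of two equal-variance ratings are independent under normality. The group effect and the two-level interaction alone therefore give 1 − 0.95² = 9.75%.

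**Sphericity.** If baseline is a time level and no correction is made (9.4.1 names none), the three-level test alone has a type I error of 5.0/5.4/7.0%.

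**The case against.** The strongest reply is that this is a drafting slip in a study that 5.5 and 9.2 call an exploratory pilot. Software would drop the constant column, the randomised comparison would remain, and 9.1 makes clear that real is to be compared with sham. The HCS is already scored relative to each patient's own baseline, so little adjustment may be lost. All of that stands, and it limits the constant covariate on its own to little more than a correction of wording.

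It does not settle the primary test. Section 9.1 names the comparison but not the term, and 6.4's interest in the trajectory could equally support an interaction. Pilot status does not remove the need to fix the term, because 9.4.1 declares significance at 5% and 9.2 says that a detected effect may support a larger study.

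A reader might infer more than the documents support:
- *That the primary comparison is biased or N = 40 is invalid.* Neither follows. Dropping the column leaves an unbiased group comparison, and the sample size does not use the covariate.
- *That the secondary ANCOVAs share the fault.* Their baseline scores (BAVQ-R, BPRS subscale, CGI, GAF) are not fixed by definition.
- *That the imaging plan as a whole cannot be run.* Only the regression on baseline HCS is affected.
- *That the compensation table in 5.5 contradicts the schema in 1.2 on when the secondary scales are rated.* The table marks a clinical assessment on the treatment day but names no scales, so it shows no conflict.

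**Conclusion.** The point holds. That baseline HCS is constant follows from section 3 and needs no assumption. The covariate in 9.4.2 adjusts for nothing, and the regression in 9.4.3 can neither be computed nor answer hypothesis 6 as written.

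The unnamed primary term has the larger consequence. For a sustained effect of the planned size, power ranges from about 5% to 89% across the three readings, and a free choice among them roughly doubles the type I error to about 10%. These figures rest on normal data, equal variances and the assumed correlations. The 5% for the two-level interaction does not depend on the correlation. The sphericity problem is minor: it is visible only at an assumed correlation of 0.9, with baseline as a time level and no correction.

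This should be fixed before unblinding. It does not call the design or the sample size into question.

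**What to change.** 1. **Section 9.4.2.** Remove baseline HCS as a covariate and state that it is 10 for all patients. Name one two-sided between-group contrast on post-treatment HCS as the primary test. One option is the real-minus-sham effect averaged over the two post-treatment ratings, adjusted for age and sex. The documents do not dictate that choice, and it costs power if the effect fades: 67/62/57% against 70/73/73% for the three-level interaction when d falls from 0.9 to 0.45. The two-level group-by-time term should not be primary, because it has no power against a sustained effect. The baseline BPRS positive subscale, already collected, may be added as a severity covariate. It uses one degree of freedom (79.2% to 79.1% power at a single rating if unrelated to HCS), and the documents give no correlation from which to judge the gain.
2. **Section 9.4.3.** Replace baseline HCS in the voxel-wise regression with post-treatment HCS as the response measure, and report the plan's own responder definition (HCS below 8) beside it. Regress it on baseline imaging either in the real arm or in both arms with a marker-by-group term. Pooling the arms without that term would find markers of later HCS whatever the treatment.

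Both changes are wording only. They need no new patients, visits or data.
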